Nevertheless, the literature on TMS for OCD remains noisy and the clinical outcomes, while promising, need improvement. An important source for this variability is the lack of individualized methods to identify and target the appropriate cortical nodes for stimulation. Our study will address this by using individual fMRI maps to identify the target and neuronavigation technology to precisely and consistently inhibit it with TMS. Another critical variable driving these inconsistencies in the field is the lack of mechanistic understanding of the effects of TMS in OCD. A priori hypotheses about disease mechanisms have driven the choices of targets of stimulations in the published clinical trials (based on a fairly robust understanding of the circuitry involved in the pathophysiology of OCD), but most studies limited themselves to measuring clinical outcomes. While this pragmatic approach is valuable, it leaves too many open questions and requires too many assumptions. Our study will innovate by proposing a translational systems neuroscience approach to understanding not only the safety and efficacy of TMS in patients with OCD, but also the physiological and anatomical changes driving (or resisting) response and remission.

II. Specific Aims

In this proposal we will apply functional neuroimaging-guided inhibitory rTMS to the pre-SMA in patients with OCD, integrating neuroimaging, behavioral and clinical research tools in a randomized controlled clinical trial. We will assess the safety and efficacy of this novel individualized strategy, study the mechanism of action at the circuit-level, and identify biomarkers and predictors of response.

Aim 1: To assess the efficacy of fMRI-guided 1HZ rTMS over the pre-SMA:

We hypothesize that patients randomized to 6 weeks of daily 1Hz rTMS will have a greater reduction in OCD symptom severity than patients randomized to identical placebo stimulation.

Aim 2: To identify the mechanisms of action of TMS at the circuit-level:

Hypothesis 2.1: We hypothesize that decreased connectivity between the pre-SMA, the Orbito-Frontal Cortex (OFC) and dorsal Anterior Cingulate Cortex (dACC) will correlate with clinical improvement.

Hypothesis 2.2: We hypothesize that TMS would improve fear extinction retention from pre- to post-treatment, and increase functional activation of the fear extinction network during extinction recall. The extinction network includes the ventromedial prefrontal cortex (vmPFC), dACC, and hippocampus.

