Aim 3: To identify biomarkers and predictors of treatment response:

Hypothesis 3.1: We hypothesize that pathological hyperconnectivity between the pre-SMA, the Orbito-Frontal Cortex (OFC) and dorsal Anterior Cingulate Cortex (dACC) will correlate with OCD symptom severity in the pre-TMS scans.

Hypothesis 3.2: We hypothesize that (a) pathological hyperconnectivity between the pre-SMA the Orbito-Frontal Cortex (OFC) and dorsal Anterior Cingulate Cortex (dACC) and (b) early reduction of this pattern after week 1 of TMS will predict positive clinical outcomes after TMS.

III. SUBJECT SELECTION

There will be two different groups of patients with OCD in this study: one will receive active stimulation and one sham stimulation (i.e. placebo). We will recruit as many patients as are needed in order to obtain 20 completers per group (i.e. 40 patients in total). We expect an early termination rate of 30%, and we will anticipate the need to recruit and consent a total of 58 patients overall.

Inclusion Criteria:

- 1) 18-65 years of age.
- 2) Proficient in English.
- 3) A diagnosis of primary OCD (as determined by SCID).
- 4) Yale-Brown Obsessive Compulsive Scale total score ≥ 16 .
- 5) Normal (or corrected) vision.
- 6) Stable OCD medication regimen or OCD medication free for \geq 12 weeks prior to study.

7) Able to give informed consent.

Exclusion Criteria:

- 1) Current or history of neurologic or psychiatric disease (e.g., mental retardation, dementia, brain damage, or other cognitive impairment) that would interfere with ability to engage in TMS
- 2) Psychopathology not appropriate for the treatment (e.g., manic episode or psychosis)
- 3) Substance abuse or dependence that is current or within the last six months or use of an illicit drug that is not prescribed, as indicated by a urine drug screen and/or clinical inference.
- 4) Use of anticonvulsants within 2 weeks prior to study (to be ruled out by a urine drug screen.
- 5) Use of Tricyclic Antidepressants (e.g. Clomipramine).
- 6) Use of psychotropic medication is allowed (except for the limitations specified on use of OCD regimens, anticonvulsants, and tricyclic antidepressants).
- 7) Documented resistance to 4 or more valid pharmacological trials of 2 or more different medication classes (e.g. SSRIs and TCAs).
- 8) Previous exposure to TMS.
- 9) Major/chronic medical conditions.
- 10) History of head injury resulting in prolonged loss of consciousness and/or neurological sequelae.

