The formal recruitment will take place at the first study visit to MGH. Necessary data will be gathered for the subject identification and remuneration, including date of birth, gender, years of education, address, telephone number, and social security number. Informed consent will be obtained by doctoral level licensed clinician study-staff or study staff that are doctoral candidates under the supervision of doctoral-level licensed clinicians prior to participation in the study using the e-consent module in REDCapTM and IRB-approved consent form. If the participant agrees to participate, the consent form will be signed electronically by the research participant and the individual obtaining consent. Each participant will be emailed a copy of the signed and dated consent form.

V. STUDY PROCEDURES

This study will have 2 phases: phase 1 will be a randomized, double-blinded, placebo-control trial, and phase 2 will be an open-label trial in which all patients who did not remit after completion of phase I (regardless of treatment group), will be invited to receive an additional 6 weeks of real TMS. Remitters will be defined as those subjects who have a week six Y-BOCS score of 12 or less.

1. Subjects Assessment

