2.1 Phase 1: Randomized placebo controlled

Patients will be randomized to receive real or sham rTMS using the variable-sized permuted blocks randomization algorithm (with a maximum block size of 4), with randomization stratified by symptom severity (Y-BOCS total score ≤31 vs. >31) and age $(\le 34 \text{ vs.} > 34 \text{ years at entry})$, to ensure balance in these factors across arms in this small study. Randomizations will be conducted in SAS using procedures outlined by Efird (2011) [Efird, J. Blocked Randomization with Randomly Selected Block Sizes. Int. J. Environ. Res. Public Health., 8, 15-20]. The randomization codes generated by our statistician/data manager for each of the 4 strata will be communicated to the study coordinator at the time of randomization (i.e. at the patient's baseline visit), based on the stratum to which the patient belongs. Patients will be blinded to their treatment arm. Patients will receive 6 weeks of daily treatments Monday through Friday (not on weekends). There will be 3 MRI sessions that will take place (i) within 2 weeks prior to the first TMS session, (ii) at the end of week 1 of treatment and (iii) within 2 weeks after the last TMS session. Longitudinal clinical assessments will take place throughout the course of study at the end weeks 2, 4 and 6 of TMS, in addition to a last assessment 3 months after TMS. Physiological assessments to measure cortical excitability and

plasticity in the motor cortex using single and paired-pulse TMS will also take place the 1st day of treatment and at the end of weeks 2, 4 and 6 of TMS.

Baseline TMS Neurophys TMS Neurophys. TMS Neurophys TMS Neurophys. 8 & 8 8 Clinical Clinical Clinical Clinical Clinical Assessment Assessment Assessment Assessment Assessment 3 mo MRI MRI MRI TMS (6 weeks) Post-TMS

Figure 1: Clinical Trial Design for Phase 1

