Subjects will view two rooms presented on a monitor, both of which differ in color and content (e.g., an office and a kitchen). The conditioned stimuli (CSs) will be different cues in the room. The CS+ and the US will only be presented in one context (conditioning context; CX+). The other context will be used for extinction training (CX-). Neither CS+ presented in the context of the CX-, nor a CS- presented in either context, will ever be paired with the US. In one of the four possible CS-CX combinations, for example, the office will serve as the dangerous context, in which the subjects will receive electric currents only when the yellow light is on, whereas the kitchen will serve as the safe context, in which no electric currents will be delivered. On day 2, subjects are placed back in the magnet and will be presented with additional extinction trials to CSs in pseudorandomorder.

As of February 27th, 2018, the fear conditioning paradigm will no longer be administered to participants in this study. All fear conditioning data collected prior to February 27th will be analyzed.

VI. BIOSTATISTICAL ANALYSIS

Analysis of Aim 1: To compare change in OCD symptom severity by treatment group, we will utilize a mixed effects linear regression model with Y-BOCS total score as the outcome, a random effect for time (study week), a fixed effect for group (rTMS versus placebo stimulation), and the interaction between time and treatment group (which is the covariate of interest). We will also control for potential confounding by any covariates that are significantly imbalanced between the treatment groups.

Analysis of Aim 2.1: Specification of the analyses examining whether decreased connectivity between the pre-SMA, the Orbito-Frontal Cortex (OFC) and dorsal Anterior Cingulate Cortex (dACC) correlates with clinical improvement can be found below, in the MRI data section - Resting state Connectivity Analysis.

Analysis of Aim 2.2: Specification of the analyses examining whether TMS improves fear extinction retention from pre- to post-treatment, and whether increased functional activation of the fear extinction network (vmPFC, dACC, and hippocampus) during extinction recall can be found below, in the MRI data section - Fear Extinction.

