Two-tensor whole brain tractography will be implemented for tract analysis. This form of tractography involves a recursive process that both fits local parameters at each step and propagates the fiber in the most stable direction, allowing simultaneous tractography and model estimation. This model also uses a covariance matrix to measure confidence, which reduces false positives, and implements two eigenvalues per voxel, which improves resolution of and accounts for branching and crossing fibers. Whole-brain tractography will be used to best account for all potential tracts among the ROIs, which may be otherwise limited in solely ROI-based tractography (Yang et al., 2014).

Power for the Primary Aim

For the primary analysis comparing change in Y-BOCS total score by treatment group, with 20 patients per group and a two-sided alpha of 0.05, we will have 90% power to detect an effect size of 1.06. Due to the novelty of our approach, no comparable data exist to inform the power calculation. However, Mantovani et al. (2010) examined change in Y-BOCS total score among 18 OCD patients (completers) randomized to 4 weeks of similar rTMS or sham treatment. Based on their reported F-statistic comparing change in Y-BOCS total score after 4 weeks of treatment, their observed effect size,

expressed as Cohen's d (Thalheimer & Cook, 2002), was 1.8. Based on these results, we believe that our study will be adequately powered to detect anticipated effect sizes.

VII. RISKS AND DISCOMFORTS

Participation in this study poses minimal foreseeable risks. Patients may experience psychological discomfort when discussing psychiatric history and/or current psychiatric symptoms or side effects. Answering detailed questionnaires may also create some inconvenience for subjects. Confidentiality of all subjects will be protected per institutional and federal requirements.

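### The Aim 1 model names time only as a random effect, so its time-by-group term does not reliably estimate the between-arm difference in Y-BOCS change

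*Combined protocol and SAP*

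**What the plan says.** The target is consistent across the document. Section II, Aim 1, hypothesises that "patients randomized to 6 weeks of daily 1Hz rTMS will have a greater reduction in OCD symptom severity" than those on sham. Section VI, Analysis of Aim 1, opens with its purpose: "To compare change in OCD symptom severity by treatment group". The paragraph on power for the primary aim begins "For the primary analysis comparing change in Y-BOCS total score by treatment group, with 20 patients per group" and claims that "we will have 90% power to detect an effect size of 1.06".

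The model is given once, in Section VI. The outcome is the Y-BOCS total score, the terms are "a random effect for time (study week), a fixed effect for group (rTMS versus placebo stimulation), and the interaction between time and treatment group", and the interaction is named as the term of interest. Time is labelled random, group is labelled fixed, and the interaction carries no label. The text does not say:
- whether there is a fixed effect of time or a patient random intercept;
- whether the random effect of time belongs to each patient or is common to all;
- whether week is continuous or categorical;
- how group is coded.

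The visit schedule is in Section V, 2.1: "Longitudinal clinical assessments will take place throughout the course of study at the end weeks 2, 4 and 6 of TMS", in addition to baseline and a visit three months after treatment.

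**The concern.** A time-by-group interaction measures the difference between arms in change only if the model also lets the reference arm change. That is the job of a fixed effect of time. A random effect with mean zero does not do it, because it describes how patients scatter around a mean slope and not what that slope is. If the mean slope is left out, the interaction can take on a different meaning, and which one depends on choices the plan does not state.

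At stake is the primary efficacy result. A sham arm is there to remove improvement that would occur without active stimulation. Under one literal reading, that improvement is counted as an rTMS effect. Under others, the test rejects too often without favouring either arm, or loses power. Analysts working from the same sentence could report different answers from the same data.

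**Working it through.** **The plan's own figure.** Inputs from the power paragraph: 20 per arm, d = 1.06, two-sided 5% level. The noncentrality is d × √(n/2) = 1.06 × √10 = 3.35. On 38 df the two-sample t-test has 90.4% power (normal approximation 91.8%). The stated 90% is reproduced, and it is the power of a two-group comparison of change.

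**Algebra, placebo = 0.** Take week as continuous and a patient-level slope u with mean zero. The model is Y = b0 + b1·group + b2·group·week + u·week + error.
- Sham mean: b0 at every week.
- rTMS mean: (b0 + b1) + b2·week.
- Hence 6·b2 estimates the rTMS arm's own six-week change, which is the sham change plus the true between-arm difference.

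Under these conditions the result does not depend on the variances.

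**Algebra, −1/+1 coding.** The two arms' slopes are forced to be −b2 and +b2. With complete, balanced data, 2·b2 still estimates the slope difference. The shared slope has no fixed term, so it goes into the random-slope variance and widens the standard error.

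**Simulation.** The setting is 20 per arm, weeks 0/2/4/6, complete data, REML, 38 denominator df and 1,000 trials per scenario (Monte Carlo error at most 1.6 percentage points). The variances are assumptions, because the documents give none. The three sets (between-patient SD, slope SD per week, residual SD) are 4.5/0.4/2.2, 4.5/0.6/3.0 and 6.0/0.8/3.6. The SD of six-week change is √(36·slope SD² + 2·residual SD²) = 3.93, 5.56 and 7.00 points. Multiplied by 1.06, this gives 4.17, 5.90 and 7.42 points.

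The 4-point shared change is for scale only. It is the gap between the entry minimum of 16 on the "Yale-Brown Obsessive Compulsive Scale total score" (Section III) and the remission cut of 12 (Section V): 16 − 12 = 4. It is not an estimate of sham response.

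Rejection with no true effect, for the three sets in order:

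| Reading | 2 shared points | 4 shared points |
|---|---|---|
| Placebo = 0, patient intercept and slope | 57 / 35 / 22% | 98 / 86 / 67% |
| Placebo = 0, patient slope only | 5 / 7 / 3% | 67 / 51 / 24% |
| Group as class, 2-df interaction, patient intercept and slope | 81 / 53 / 32% | 100 / 98 / 91% |

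Two readings are valid: adding fixed time, or testing the 1-df difference between the two group slopes, each with a patient random intercept. They span the same fixed effects and gave the same results: 3.7–6.5% rejection and bias of at most 0.1 point.

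Power with a true benefit of 1.06 SD and 4 shared points:

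| Model | Power |
|---|---|
| Fixed time, patient intercept and slope | 92 / 93 / 92% |
| −1/+1 coding, no fixed time, patient intercept and slope | 36 / 60 / 65% |
| Fixed time, no random intercept | 27 / 61 / 52% |

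In the same scenario, placebo = 0 coding gives estimates of −8.2 / −9.9 / −11.4 points, which is the true benefit plus 4.

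**A second variance set** (between-patient SD 5, slope SD 0.75, residual SD 2.5; SD of change 5.7; 400 trials) agrees. With no true effect and 0, 2, 4 or 6 shared points, placebo = 0 coding with patient intercept and slope gives estimates of 0.0, −2.1, −4.0 and −6.0, and rejects 3.5%, 36.5%, 81% and 97%.

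**Random week effect common to all patients.** This can absorb shared change.
- Common random week slope alongside the patient effects, placebo = 0, middle set, 300 trials: bias −0.7 and −0.4 points, with 16% and 7% rejection, at 2 and 4 shared points.
- Week as a crossed random factor, second set, only 60 trials: bias −0.3 to −1.2 points with 25–33% rejection at 2 to 6 shared points, and 13% rejection with none.

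**The case against.** The strongest reply is that a random effect for time is common shorthand for patient slopes varying around a fixed mean slope. The purpose is stated, the interaction is named as the term of interest, and the hypothesis and power paragraph point the same way. The harmful result needs continuous week, placebo coded 0 and a deliberate omission of the mean slope, and the text commits to none of these. This stands as a limit: the sentence may be incomplete wording around a sound intention. It does not remove the point, because the shorthand reading is not written down anywhere and the sentence takes care to label its terms as fixed or random.

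A reader might infer that the interaction must equal the rTMS arm's own change whatever the variances. The documents do not support that. It requires the random effect to be patient-level with mean zero, and the plan does not say that it is. With a week effect common to all patients the bias is much smaller, although over-rejection can remain.

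It is also fair that the unbiasedness of −1/+1 coding was shown only for complete, balanced data, whereas Section III expects 30% early termination. Finally, the sizes depend on assumed variances and sham response. With no shared change, the placebo = 0 model with patient intercept and slope is unbiased and rejects 3.5% of the time in the second variance set.

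**Conclusion.** The concern holds: as written, the Aim 1 terms do not pin down a test of the between-arm difference in change. With a zero-mean patient slope, continuous week and placebo coded 0, the bias equals the sham arm's own change. With a common week effect, the bias is smaller but the test can still over-reject. With −1/+1 coding and complete data, the estimate is unbiased but power can fall well below that of the model with fixed time. The test is valid if the authors meant a patient slope around a fixed mean slope, or the 1-df difference in group slopes, with a patient random intercept.

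The algebra is exact under its stated conditions. Every rejection rate and power loss is illustrative. A reader might also infer that the trial is underpowered or its sample size wrong. That does not follow: the 90% figure is reproduced at 90.4% as a two-group comparison, does not depend on the mixed model, and needs no restating once the model is corrected.

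**What to change.** Restate the Aim 1 model with fixed effects for time, group and time-by-group, plus a patient-level random intercept and slope. Categorical visit with unstructured within-patient covariance is an acceptable alternative. Say whether week is continuous or categorical. Name the active-minus-sham difference in Y-BOCS change from baseline to week 6 as the tested contrast; the result then no longer depends on how group is coded. The random intercept should be written in along with fixed time, since fixed time with a patient slope alone left the simulated test very conservative (0.0–0.4% rejection under no effect).

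The cost is one or two sentences in Section VI. No new data or patients are needed, and the sample size does not change.

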All candidates for this project will undergo a comprehensive clinical evaluation including a clinical interview to establish relevant psychiatric, medical and neurological history and a structured clinical interview (Structured Clinical Interview for DSM-IV Axis I Disorders; SCID-I) to confirm psychiatric diagnoses, the Edinburgh Handedness Inventory – Short Form (EHI) to establish handedness, the Beck Depression Inventory (BDI), HAM-D, and PHQ-9 to quantify depressive symptoms, the Beck Anxiety Inventory (BAI) to quantify general anxiety symptoms, the Speilberger State Trait Anxiety Inventory (STAI) to quantify trait vs. state aspects of anxiety, the Anxiety Sensitivity Index (ASI) to quantify anxiety sensitivity, and a covid-19 impact scale to assess the effect of the coronavirus pandemic in the past week. The Yale Brown Obsessive-Compulsive Scale (YBOCS), Obsessive-Compulsive Beliefs Questionnaire-44 (OBQ), the Compulsive Behaviors Form (CBF), and Obsessive-Compulsive Inventory (OCI-R) will be used to measure OCD symptoms and severity. The Clinical Global Impressions (CGI) rating scale will be used as an additional measurement of clinical change from baseline (see detailed description below). In addition, the Rey-Osterrieth Complex Figure Test and the Stroop and Wisconsin Card Sorting tasks will be conducted to assess relevant aspects of executive function and selective attention (see detailed description below). The initial evaluation of all subjects will be audio recorded for interrater reliability, and therapist supervision purposes. The digital recordings will contain participant ID numbers but not names or other identifying information. Digital recordings will be rated and simultaneously entered in the REDCap data management system for

analysis. The digital recordings will be kept by the research team in a password-protected file and destroyed after completion of the study. When possible, assessments will be used from previous studies in the OCD program (to which participants will consent).

After the initial thorough baseline assessment, patients will be assessed longitudinally through the course of the study at weeks 2, 4, 6 and 3 months after the last TMS session. These assessments will be shorter and will include the following measures: YBOCS, OBQ, OCI-R, BDI, HAM-D, PHQ-9, and covid-19 impact scale. The Rey-Osterrieth Complex Figure Test and the Wisconsin Card Sorting and Stroop tasks will also be conducted at week 6.

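### The Aim 1 model, as written, permits a single straight-line slope through weeks 0 to about 19, in which the 3-month visit outweighs the end-of-treatment difference

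*Combined protocol and SAP*

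**What the plan says.** **Model.** Section VI, Analysis of Aim 1, specifies a linear mixed model for Y-BOCS total with "a random effect for time (study week), a fixed effect for group (rTMS versus placebo stimulation), and the interaction between time and treatment group". The interaction is singled out as the term "which is the covariate of interest". No visit, contrast or time point is named.

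**Schedule.** Section V.1 says that "patients will be assessed longitudinally through the course of the study at weeks 2, 4, 6 and 3 months after the last TMS session", and the follow-up battery includes Y-BOCS: "These assessments will be shorter and will include the following measures: YBOCS, OBQ, OCI-R, BDI, HAM-D, PHQ-9, and covid-19 impact scale". Section V.2.1 lists the Phase 1 clinical assessments at the ends of weeks 2, 4 and 6, "in addition to a last assessment 3 months after TMS".

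**Hypothesis.** Aim 1 in section II expects that "patients randomized to 6 weeks of daily 1Hz rTMS will have a greater reduction in OCD symptom severity" than those given placebo stimulation. Six weeks is the length of treatment here; no assessment time is given.

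**Power.** With 20 per group and two-sided alpha 0.05, "we will have 90% power to detect an effect size of 1.06". The quantity powered is change in Y-BOCS total, with no week attached. The benchmark effect of 1.8 comes from a 4-week change in an earlier trial.

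**Crossover.** The introduction to section V and section V.2.2 offer open-label active TMS to non-remitters of both arms after Phase 1. Remission is defined on the week-6 Y-BOCS.

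**The concern.** A random effect for study week is ordinarily a random slope, which needs numeric time. A categorical visit over five visits would give four interaction terms, not one. So the text points to a single slope difference, with the arm effect growing at a constant weekly rate for as long as data are included.

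Treatment stops at week 6. An effect that builds over six weeks and then holds or fades is not a straight line out to week 19. Forcing the late visit onto the same line changes what the primary coefficient measures: it becomes mostly a comparison of the 3-month value with the early visits. By 3 months, non-remitting sham patients may have received active treatment, so convergence of the arms is plausible by design. The functional-form problem remains even without any crossover.

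At stake are the meaning of the primary estimate and whether the trial has the power it states.

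**Working it through.** **1. The plan's own figure.** Inputs from Power for the Primary Aim: n = 20 per arm, d = 1.06, alpha 0.05 two-sided. For a two-sample t-test of one change score per patient, the noncentrality is d√(n/2) = 1.06 × √10 = 3.35 on 38 df, giving power of 90.4%. The stated 90% is reproduced.

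**2. Slope weights.** Y-BOCS visits are at weeks 0, 2, 4, 6 and 6 + about 13 = 19. The mean is 31/5 = 6.2.

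- Deviations: -6.2, -4.2, -2.2, -0.2, +12.8.
- Squares: 38.44, 17.64, 4.84, 0.04, 163.84; sum 224.8.
- Shares of the sum of squares: 17%, 8%, 2%, 0.02%, 73%.
- Least-squares weights (deviation/224.8): -0.0276, -0.0187, -0.0098, -0.0009, +0.0569.

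Week 19 has leverage 1/5 + 163.84/224.8 = 0.93 (0.92 or 0.94 if the visit falls at week 18 or 20).

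**3. What the slope recovers.** Let the arm difference be 0, D/3, 2D/3, D at weeks 0 to 6 and hD at week 19, where h is the share kept (assumed). Then

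slope difference = D(-1.400 - 1.467 - 0.200 + 12.8h)/224.8 = D(12.8h - 3.067)/224.8.

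Six times the slope, as a fraction of D:

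- h = 1: 6 × 9.733/224.8 = 0.26
- h = 0.5: 6 × 3.333/224.8 = 0.09
- h = 0.25: 6 × 0.133/224.8 = 0.004
- h = 0: 6 × (-3.067)/224.8 = -0.08

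These least-squares ratios need no SD. With weights optimal for serially correlated errors they become up to 0.30, 0.14, 0.06 and -0.02.

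**4. Power of the slope test.** The documents give no SD, correlation or durability figure, so the covariances below are assumptions. All cases take 20 complete patients per arm, a fixed time effect alongside the random one, linear build-up, and a week-6 difference of 1.06 SD of change.

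Worked case: compound symmetry, unit SD, correlation 0.5, so the SD of change is √(2 × 0.5) = 1 and D = 1.06.

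- All visits, h = 1: slope difference 1.06 × 9.733/224.8 = 0.0459; SD of a patient's slope √(0.5/224.8) = 0.0472; ratio 0.97; power 85%.
- All visits, h = 0.5: ratio 0.33; power 18%.
- Weeks 0-6 only (sum of squares 20): slope difference 1.06/6 = 0.177; SD √(0.5/20) = 0.158; ratio 1.12; power 93%.

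| Assumed covariance | Fully kept | Half kept | None kept |
|---|---|---|---|
| Compound symmetry, 0.5 | 85% | 18% | 16% |
| Exponential decay, 0.9 per week | 49-64% | 10-19% | 5-9% |
| Decay 0.95 per week plus visit-level error | 55-65% | 11-17% | 6-10% |
| Random intercept SD 0.8, slope SD 0.05, residual 0.5 | 44% | 10% | 9% |
| Same, slope SD 0.10 | 24% | 7% | 7% |
| Patient response that follows the mean shape: SDs 4 (intercept), 4 (response), 2.5 (residual) | 89% | 32% | 29% |

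Where a cell shows a range, its ends come from least-squares weights and from weights optimal for that covariance. The last row is from 4,000 simulated trials per shape; a closed-form check gives 88%, 31% and 27%. With none kept the expected slope has the wrong sign, so those rejections are mostly in the wrong direction. For the first five rows, the slope over weeks 0-6 alone has 90-93% power.

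**The case against.** The strongest reply is that the decisive premise is not written down. The schedule sections list assessments and do not define the analysis set. The follow-up is described as 3 months after TMS, never as a numbered study week, so a term in study week could be meant for the treatment weeks only. On that reading the slope agrees with the stated power and the problem largely disappears. This stands as a limit on the claim. It does not remove it: section V.2.1 counts the 3-month visit among the Phase 1 longitudinal assessments and the Aim 1 analysis excludes nothing, so an analyst following the text would include it.

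A reader might also infer that Aim 1 and the power statement promise a 6-week difference. They do not. Aim 1 gives a treatment duration and the power text gives change without a week. That week 6 is the intended endpoint is an inference from the treatment period and the week-6 remission definition.

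A reader might further infer that power is lost whenever the late visit is included. That is too strong. In the simulated setting with the benefit fully kept, power is 89% for linear build-up and 93% for late onset, although it is 77% for early onset. The steep losses need either partial loss of benefit by 3 months or patient slopes that vary widely.

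Two smaller points also stand. The plan never proposes to report six times the slope; that multiple is used here only to show what the coefficient tracks. And for patients who enter Phase 2, the follow-up visit may not fall at week 19, so the 73% describes an idealised schedule.

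**Conclusion.** The concern holds in conditional form. The plan does not fix the visits in the primary model, the form of time, or the time point of the contrast. Its natural reading is one linear slope with no visit excluded. Under that reading the tested coefficient does not track the end-of-treatment difference, and power ranges from close to the stated figure to far below it, depending on durability and covariance that the documents do not give.

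The leverage figure rests only on the schedule, with 3 months taken as about week 19. The recovery fractions also assume linear build-up to week 6 and a share kept at 3 months, and the power ranges add assumed covariances. The documents do not support saying that the 90% is miscalculated: it is right for one change score. Nor do they support saying that the 3-month visit certainly enters the model.

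This is more than a request for detail. Two analysts could follow the same text and obtain materially different primary results, and the remedy costs very little.

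**What to change.** Enter visit as a categorical fixed effect with a visit-by-arm interaction. Name the active-minus-sham difference in change from baseline to week 6 as the primary test, and say that the power statement refers to it. Report the 3-month contrast separately, with a note that open-label treatment may have intervened. Settle this before unblinding.

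At minimum, state that the primary slope model uses weeks 0, 2, 4 and 6 only. That alone removes the influence of the late visit, and categorical time is then a further safeguard against a non-linear response within the six weeks.

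The cost is wording and a few degrees of freedom. If the effect is truly linear over weeks 0-6, the week-6 contrast gives up about 1 point of power against the weeks 0-6 slope (91.2% against 92.4% in the simulated setting).
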